**Table 2: Clinical and Pathologic Features of the Four Principle Liposarcoma Subtypes\***

| Subtype                       | Well-differentiated   | Dedifferentiated   | Myxoid  | Pleomorphic   |
|-------------------------------|---|--|---|---|
| Percent of liposarcoma | 40-50   | 15-20  | 20-30   | 5-10  |
| Age (years)            | 50-60   | 50-60  | 30-50 (also childhood/adolescence)  | >50   |
| Morphology             | Pleomorphic mature adipocytes, variable numbers of lipoblasts               | High-grade pleomorphic sarcoma on well-differentiated background         | Round/oval mesenchymal cells plus signet ring lipoblasts within myxoid stroma | Variable pleomorphic lipoblasts on background of high-grade pleomorphic sarcoma |
| Typical sites          | Extremities; retroperitoneum; paratesticular (rare); mediastinum (rare)     | Retroperitoneum; extremities; paratesticular; mediastinum; head and neck | Thigh; other proximal extremities   | Limbs   |
| Recurrence             | Local recurrence (retroperitoneum > extremities); Rare metastatic potential | Local recurrence in ~ 40%; Metastasis (lung) ~ 20%-30%                   | Local and/or metastatic (bone, soft tissue, serosa) ~ 40%                     | Local recurrence ~ 30%-50%; Metastasis (lung) ~ 30%-50%                         |
| Response to therapy    | Poor  | Poor   | Generally sensitive to radiotherapy and chemotherapy                          | Variable chemosensitivity   |
| Genomics               | 12q13-15 amplification  | 12q13-15 amplification plus other chromosomal abnormalities              | t(12;16) with FUS-DDIT3 fusion  | Complex, with multiple chromosomal abnormalities and higher mutation rate       |

\*Adapted from Lee et al.

Initial treatment for liposarcoma depends on the type, size and location of the tumor. If feasible, surgery is often attempted, but the option of surgery may be limited by tumor location, invasion of critical structures (e.g., adjacent organs or major blood vessels) or evidence of metastases. Adjuvant chemotherapy may be considered in subjects with locally invasive tumors or for tumors with high metastatic potential (e.g., MLS, PLS). Nomograms have been developed that provide prognostic information to subjects undergoing surgery for liposarcoma.

A number of chemotherapy drugs are used for soft tissue sarcomas (e.g., gemcitabine, docetaxel, dacarbazine), but doxorubicin and ifosfamide remain the most effective agents. Systemic chemotherapy including an anthracycline has been reported to have only a modest response rate of 12% in soft tissue sarcomas with a median progression-free survival of 4.6 months and a median overall survival of 15.2 months.

Trabectedin (Yondelis), and alkylating agent, was approved in 2015 for unresectable or metastatic liposarcoma or leiomyosarcoma in subjects who had received a prior anthracycline-containing regimen. Trabectedin was approved based on an improvement in progression-free

survival compared with dacarbazine (4.2 vs 1.5 months) despite no observed improvement in overall survival.

Eribulin (Halaven), a microtubule polymerization inhibitor, was approved in 2016 for unresectable or metastatic liposarcoma in subjects who had received a prior anthracycline. The approval was based on a 7-month improvement in survival (15.6 months with eribulin vs. 8.4 months with dacarbazine). The improvement in OS was only statistically significant for advanced/metastatic DDLS and pleomorphic liposarcoma.

## 1.2 Cyclin-Dependent Kinases 4 and 6 (CDK4/6)

[figure not shown]
Cyclin-dependent kinases (CDKs), part of the serine/threonine protein kinase family, drive cell-cycle progression, control transcriptional processes, and regulate cell proliferation. CDK4/6 blocks the transition from the G1 to S phase of the cell cycle by blocking Rb phosphorylation and E2F release. Overexpression of the CDK4 protein leads to Rb (retinoblastoma) phosphorylation and progression in the cell cycle. Based on these effects, dysregulation of CDKs is considered to play a key role in tumorigenesis. CDK4/6 genes are widely expressed among various tumors, and high or moderate expression of CDK4/6 is commonly associated with poor survival. No CDK4/6 inhibitors are FDA-approved for the treatment of liposarcoma, however, several are approved for the treatment of post-menopausal hormone receptor-positive/human epidermal growth factor receptor 2 (HER2)-negative metastatic breast cancer including palbociclib (2015), ribociclib (2017) and abemaciclib (2018).

CDK4 is considered a potential target in WDLS/DDLS based on the amplification of CDK4 in >90% of these liposarcomas. Abemaciclib, a CDK 4/6 inhibitor, has been studied in a single-arm Phase 2 study in subjects with dedifferentiated liposarcomas where it demonstrated promising progression-free survival of 12 weeks in 76% of subjects. Median PFS was 30.4 weeks, and one subject had a partial response. Grade 3-4 toxicities included anemia (37%), neutropenia (20%), thrombocytopenia (17%) and diarrhea (7%). Similar results were reported in WDLS/DDLS patients with palbociclib treated on two different intermittent dosing regimen.

## 1.3 SPH4336

SPH4336 is a novel, highly selective CDK4/6 inhibitor currently being studied in a Phase 1 study in patients with solid tumors in China. The structure of SPH4336 is shown in Figure 1.

**Figure 1: Chemical Structure of SPH4336**

### **1.3.1 Preclinical Safety Pharmacology and Toxicology**

The selectivity of SPH3643 (free base of SPH4336) against 30 kinases was compared with abemaciclib and palbociclib. SPH3643 showed better selectivity for CDK4/6 relative to activity against CDK7/9/1/2. SPH3643 had an IC50 greater than 300 nmol/L against a number of other kinases, except PKC $\alpha$  (73 nmol/L), FLT3 (75 nmol/L), and GSK3 $\beta$  (88 nmol/L) and supports the observation that SPH3643 is a highly selective inhibitor of CDK4/6.

After a single intravenous administration in rats, SPH3643 exhibited a moderate plasma t1/2 (~5.5 h), high plasma clearance and apparent volume of distribution. After oral administration in rats, SPH3643 produced more than dose-proportional increases in exposure and t1/2 (~7-19 h). Oral bioavailability was ~20% at higher doses with no apparent difference in the fed or fasted state. Multiple oral dosing resulted in accumulation in rats. After a single intravenous administration in cynomolgus monkeys, SPH3643 exhibited a long plasma t1/2 (~11 h), high plasma clearance and apparent volume of distribution. Oral bioavailability was ~30% and no accumulation was observed with repeated oral dosing.

Plasma protein binding of SPH3643 in several species, including humans, was high and ranged from 87 to 97%. SPH3643 was highly metabolized and eliminated mainly by phase I metabolic reactions (demethylation, dehydrogenation, and oxidation), predominately by CYP3A4. SPH3643 had minimal inhibitory activity on most CYP450 isoforms and moderate inhibitory activity on CYP2B6. There was no indication of any induction of human CYP1A2, CYP2B6 or CYP3A4.

SPH3643 was generally well-tolerated in rats and monkeys with most drug-related findings being reversible. NOAELs of 30 and 10 mg/kg po were established for SPH3643 in the GLP 4-week rat and monkey toxicology studies, respectively. No significant differences in toxicity profile were noted between SPH3643 (free base) and SPH4336 (maleate salt) at a dose of 100 mg/kg po in a bridging GLP 4-week repeat-dose toxicity test in rats. Target organs were the

digestive (e.g., epithelial cell proliferation and macrophage infiltration in digestive tract), hepatic (e.g., liver enzyme elevations), hematologic (e.g., anemia) and immune systems (e.g., decreased bone marrow hematopoietic cells), consistent with the toxicities reported for other CDK4/6 inhibitors. Safety margins of approximately 0.5-fold to 3.6-fold (based on body surface area scaling) over a projected daily human dose of 400 mg SPH4336 given orally were established in these nonclinical studies.

### **1.3.2 Preclinical Efficacy**

Studies of SPH3643 in a variety of xenograft models across a spectrum of CDK4-positive tumors (breast, colon, ovarian, lung, glioma, leukemia, liver, liposarcoma) demonstrated antitumor activity that was better or comparable with abemaciclib and palbociclib.

## **1.4 Prior Clinical Experience**

SPH4336 is currently under investigation as monotherapy in a Phase 1 dose escalation trial in China (Study SPH4336-101) for subjects with advanced solid tumors. Interim safety reports from the initial dose cohorts (50, 100, 200, 300, 400, 600 mg) show SPH4336 to be generally well-tolerated with no DLTs and adverse events typical of CDK4/6 inhibitors (e.g., anemia, leukopenia, lymphopenia, neutropenia, transaminitis, diarrhea).

## **1.5 Rationale for the Study**

SPH4336 is considered appropriate for study in humans based on the following:

- CDK4 is a validated target in human tumors with several CDK4/6 inhibitors approved for the treatment of various solid tumors;
- CDK4 is considered a potential target in WDLS/DDLS based on the amplification of CDK4 in > 90% of WDLS/DDLS tumors;
- SPH4336 is a highly selective inhibitor of CDK4/6 with pharmacologic properties (e.g., increased exposure) that may result in an improved therapeutic index compared to currently available CDK4/6 inhibitors;
- Preclinical studies have demonstrated a safety profile of SPH3643 and SPH4336 consistent with other CDK4/6 inhibitors;
- Xenograft models have demonstrated antitumor activity of SPH3643 and SPH4336 at exposures that should be achievable in the clinic; and,
- Interim PK and safety data from an ongoing Phase 1 trial of SPH4336 in China support a dose of 400 mg in liposarcoma patients.

## **1.6 Dose of SPH4336**

SPH4336 is under evaluation in China in an ongoing Phase 1, open-label, dose-escalation clinical study to evaluate the safety, tolerability, pharmacokinetics, and preliminary efficacy of SPH4336 tablet monotherapy in patients with advanced solid tumors (Study SPH4336-101). Interim PK data from the first 6 dose cohorts (50, 100, 200, 300, 400, 600 mg) show that QD oral dosing of SPH4336 generally produced dose-related increases in exposure with increasing dose,

although plasma concentrations appear to plateau at the 400 mg dose. Accumulation was observed with repeated dosing, reaching steady-state within approximately 2 weeks of daily dosing. The ratio of  $C_{trough}$  400 mg QD (at steady-state)/IC50 CDK4 SPH3643, adjusted for PPB (Plasma Protein Binding) *in vitro* was approximately 6.6. A similar ratio was observed for abemaciclib (Verzenio®) at its approved dose of 200 mg BID. This suggests that significant inhibition of CDK4 is achieved at trough concentrations following multiple doses of  $\geq$  400 mg SPH4336.

Taken together, the interim PK and clinical safety data from the ongoing Phase 1 study along with the nonclinical safety package, support a dose of 400 mg QD in this Phase 2 study in liposarcoma patients. Clinical benefit/efficacy is best addressed in this Phase 2 study in a patient population (dedifferentiated and well-differentiated/dedifferentiated liposarcomas) expressing the drug target (CDK4).

## 1.7 Potential Risks and Benefits

### 1.7.1 Potential Risks

With limited human experience, the potential risks associated with SPH4336 are based on animal data and the safety profile of other CDK4/6 inhibitors. These risks include:

- GI Toxicity (e.g., nausea, diarrhea)
- Hepatic toxicity (e.g., transaminase elevations)

- Constitutional symptoms (e.g., fatigue)
- Hematologic toxicity (e.g., called leukopenia, lymphopenia, neutropenia, anemia, thrombocytopenia)

In addition, given the limited clinical experience with SPH4336, there may be risks that are not currently known.

### **1.7.2 Potential Benefits**

Information gained from the study may help other people with locally advanced or metastatic liposarcoma in the future. SPH4336 may benefit subjects by reducing tumor volume and/or slowing tumor growth. A significant extension of Progression-Free Survival (PFS), as seen with other drugs acting through the same mechanism, may be observed. In subjects with symptoms related to the presence of a tumor, SPH4336 may result in a reduction in symptoms.

## **2 STUDY OBJECTIVES AND ENDPOINTS**

### **2.1 Objectives**

#### **2.1.1 Primary Objectives**

- To evaluate the efficacy of SPH4336 in subjects with CDK4-positive liposarcomas

#### **2.1.2 Secondary Objectives**

- To evaluate the safety profile of SPH4336
- To evaluate the pharmacokinetics of SPH4336
- To evaluate other tumor responses
- To evaluate various tumor tissue biomarkers for activity

### **2.2 Endpoints**

#### **2.2.1 Primary Endpoint**

- Progression-Free Survival (PFS) as assessed by the Investigator at 12 weeks

#### **2.2.2 Secondary Endpoints**

- Type, incidence, severity (as graded by the National Cancer Institute Common Terminology Criteria for Adverse Events [NCI CTCAE] v5.0), seriousness and relationship to study medications of AEs and any laboratory abnormalities
- Pharmacokinetics include plasma concentration-time profiles and  $C_{max}$ ,  $T_{max}$ ,  $AUC_{last}$ ,  $AUC_{inf}$ ,  $t_{1/2}$ ,  $CL/F$ ,  $Vss/F$ , Accumulation Ratio for  $C_{max}$ ,  $AUC$ , as appropriate
- Median PFS, Best Overall Response (BOR), Time to Response (TTR), Duration of Response (DOR), Overall Survival (OS), and other efficacy assessments
- Tumor tissue biomarkers (e.g., phospho-Rb, Ki-67) in the first 10 patients

### 3 SUBJECT POPULATION

#### 3.1 Inclusion Criteria

- Informed consent
- $\geq 18$  years of age
- ECOG performance status 0 or 1
- Histologically confirmed, locally advanced or metastatic sarcoma
  - Dedifferentiated or well-differentiated/dedifferentiated liposarcomas
- No more than 3 prior lines of treatment
- Evidence of progression as evidenced by at least one of the following within the past 3 months:
  - An increase of at least 20% in measurable tumors
  - The appearance of new lesions
  - Unequivocal progression of non-measurable lesions
- Measurable disease per RECIST v1.1
- If residual treatment-related toxicity from prior therapy:
  - All treatment-related toxicity resolved to Grade 1 or baseline (alopecia excepted)
- ANC  $\geq 1,500/\mu\text{L}$
- Platelets  $\geq 100,000/\mu\text{L}$
- Hgb  $\geq 9.0 \text{ g/dL}$  (in the absence of pRBC transfusion over the prior 4 weeks)
- Estimated glomerular filtration rate of  $\geq 60 \text{ mL/min}$  (based on the Cockcroft and Gault formula for individualized estimates of GFR^3)
- Total bilirubin  $\leq 1.5 \times$  the Upper Limit of Normal (ULN) or  $\leq 3 \times$  ULN if known Gilbert's disease
- AST and ALT  $\leq 3 \times$  ULN or  $\leq 5 \times$  ULN if malignant involvement of the liver
- Sterile or willing to use effective contraception (approved hormonal contraceptive such as oral contraceptives, patches, implants, injections, rings or hormonally-impregnated intrauterine device (IUD), or an IUD in women of childbearing potential and a condom in men) during the study and for 3 months following the last dose of study drug
- Availability of archived tumor tissue or willingness to undergo a baseline tumor biopsy, and in the first 10 study subjects, to determine baseline tumor biomarker levels and a willingness to undergo a second tumor biopsy at C1D15 to assess treatment-induced changes in tumor biomarker levels

#### 3.2 Exclusion Criteria

- Prior treatment with a CDK4/6-targeted agent
- Patient's tumor known to be CDK4 negative
- Anticancer therapy (e.g., chemotherapy, biologics, irradiation) within 14 days or 5 half-lives (whichever is greater) of screening

- Major surgery within 28 days of screening
- Requirement for systemic treatment with strong CYP3A4 inhibitors or inducers of CYP3A4 at study entry
- Central nervous system metastases or leptomeningeal disease, unless appropriately treated and neurologically stable without steroids for  $\geq$  28 days
- Other malignancy unless disease-free for  $\geq$  2 years and not expected to relapse or require treatment during study participation
- Active systemic infection or severe localized infection
- Known HIV-positive with CD4+ cell counts  $<$  350 cells/uL or a history of an AIDS-defining opportunistic infection
- Known hepatitis B virus (HBV) or hepatitis C virus (HCV) infection with viral load above the limit of quantification
- Active COVID-19 infection
- Major cardiac abnormalities (e.g., uncontrolled angina, unstable arrhythmias, myocardial infarction, NYHA Class  $\geq$  3 CHF)  $\leq$  6 months of C1D1
- Persistent (3 ECGs  $\geq$  5 mins apart) prolongation of the QTcF (Fridericia)  $>$  470 msec
- [Females] Pregnant or nursing
- Any other medical or psychiatric condition, or laboratory abnormality that would result in an unacceptable risk with study participation
- Presence of active gastrointestinal disease or other condition expected to interfere significantly with absorption, distribution, metabolism or excretion of oral therapy (e.g., ulcerative disease, uncontrolled nausea, vomiting, chronic diarrhea, malabsorption syndrome)

## 4 STUDY DESIGN

This is a multicenter, non-randomized, open-label Phase 2 study of SPH4336 in subjects with CDK4-positive liposarcomas.

SPH4336 will be administered orally once each day in successive 28-day cycles until demonstration of progressive disease or the development of unacceptable toxicity.

The study will incorporate a safety lead-in for the initial 10 subjects. Safety will be evaluated after 10 subjects (minimum 1 cycle completed) are accrued to allow a full assessment of safety by a Safety Review Committee (SRC). The study will be stopped if unacceptable toxicity is observed in more than 2 subjects based on SRC recommendation.

Tumor assessments according to RECIST v1.1. will be performed at baseline and every 6 weeks (from C1D1) for 36 weeks, then every 12 weeks thereafter. PK samples will be collected in all subjects. Baseline (pretreatment) tumor tissue will be collected from all subjects to confirm histologically a liposarcoma with a dedifferentiated component and CDK4 positivity, and in the

first 10 study subjects, tumor tissue biomarkers (phospho-Rb, Ki-67) will be analyzed in baseline (pretreatment) and C1D15 tumor tissue samples.

A Safety Review Committee (SRC) will oversee study safety and will meet at a frequency commensurate with accrual during the study (e.g., after 10 subjects (safety lead-in) and 20 subjects, and as needed).

#### **4.1 Safety Lead-In**

The study will incorporate a safety lead-in for the initial 10 subjects. Safety will be evaluated after 10 subjects (minimum 1 cycle completed) are accrued to allow a full assessment of safety by a Safety Review Committee (SRC). The study will be stopped if unacceptable toxicity is observed in more than 2 subjects based on SRC recommendation.

#### **4.2 Unacceptable Toxicity**

To be considered as unacceptable toxicity, an AE must meet each of the following 2 criteria:

- Occur during the first 28 days of SPH4336 administration
- Not be incontrovertibly related to underlying disease

In addition, an AE must meet at least one of the following criteria:

- Any Grade 4 AE
- Any Grade 3 non-hematologic AE
- Any AE that results in permanent treatment discontinuation

The following are excluded from the definition of unacceptable toxicity:

- Grade 4 anemia or neutropenia that resolves within 14 days and which is not expected to recur based on a treatment modification (e.g., use of erythrocyte or neutrophil growth factors)
- Grade 4 lymphopenia
- Grade 3 headache, nausea, vomiting, diarrhea, fatigue, or pain if controlled within 72 hours
- Grade 3 electrolyte abnormalities that are asymptomatic and resolve to at least Grade 2 within 72 hours

The SRC will have the option of declaring other toxicities not listed above as unacceptable, if necessary, to ensure subject safety.

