#### **4.7 Discontinuation of SPH4336 Administration**

SPH4336 may no longer be administered to a subject in the event of any of the following:

- Clinically and/or radiologically significant progressive disease;

- Unacceptable adverse event(s) considered secondary to SPH4336 despite appropriate therapy;
- Withdrawal of consent for SPH4336 administration by the subject (subject may agree to continued follow-up for safety and long-term outcome endpoints);
- Noncompliance by the subject as determined by the Investigator with agreement from the Medical Monitor; or,
- Termination of study by the Sponsor.

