**Table 3: Dose Hold Secondary to SPH4336-related Toxicity**

| Toxicity (CTCAE Grading)       | Dose Hold   | Dose modification on resumption  |
|--------------------------------|---|--|
| 1 or 2                  | No dose hold required   | None   |
| 3                       | Hold dosing until toxicity has resolved to at least Grade 1 or baseline                                       | First occurrence (of same AE): No dose reduction
Second occurrence: Reduce dose by at least 100 mg
Third occurrence: Permanently discontinue |
| 4 anemia or neutropenia | Restart dosing only if recovery to $\leq$ Grade 1 occurs in $\leq$ 14 days, otherwise permanently discontinue | First occurrence (of same AE): Reduce by at least 100 mg
Second occurrence: Permanently discontinue   |
| 4 lymphopenia           | Hold dosing until toxicity has resolved to at least Grade 1 or baseline                                       | First occurrence (of same AE): Reduce by at least 100 mg
Second occurrence: Permanently discontinue   |
| 4 (non-hematologic)     | N/A, permanently discontinue  | N/A, permanently discontinue   |

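### The unconditional Grade 4 lymphopenia exclusion in Protocol 4.2 leaves a treatment-ending Grade 4 lymphopenia out of the lead-in count, although a treatment-ending Grade 3 lymphopenia is counted

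*Protocol*

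**What the plan says.** Protocol 4.2 defines unacceptable toxicity in three steps. The event must arise in the first 28 days of dosing and must not be clearly due to the disease itself. It must then meet one of three criteria: any Grade 4 event, any Grade 3 non-hematologic event, or "Any AE that results in permanent treatment discontinuation". Finally, under the words "The following are excluded from the definition of unacceptable toxicity", four kinds of event are taken out of the definition as a whole:

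- "Grade 4 anemia or neutropenia that resolves within 14 days and which is not expected to recur based on a treatment modification";
- "Grade 4 lymphopenia";
- certain Grade 3 symptoms, if controlled within 72 hours;
- asymptomatic Grade 3 electrolyte abnormalities, if back to at least Grade 2 within 72 hours.

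Only the lymphopenia entry has no condition. Section 4.2 closes with a discretionary clause: "The SRC will have the option of declaring other toxicities not listed above as unacceptable".

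The definition feeds the lead-in rule for the first 10 subjects in 4.1: "The study will be stopped if unacceptable toxicity is observed in more than 2 subjects based on SRC recommendation".

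For both Grade 3 toxicity and Grade 4 lymphopenia, Table 3 says: "Hold dosing until toxicity has resolved to at least Grade 1 or baseline". Section 6.6.2 permits restart only if no more than 21 days have passed since the last dose and the event is not expected to recur at the same grade. Section 4.7 separately allows discontinuation for "Unacceptable adverse event(s) considered secondary to SPH4336 despite appropriate therapy".

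**The concern.** The third criterion treats permanent loss of treatment in the first cycle as a signal whatever the grade. The exclusion list overrides that criterion along with the grade criteria. For three of the four entries the recovery or control condition confines the exclusion to events that were managed. The lymphopenia entry has no such limit, so it also removes an event that did not recover and ended treatment. The more severe form of one toxicity is then left out while its milder form is counted.

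At stake is a count with a low threshold. The stop is at more than 2 of 10 subjects, so one uncounted discontinuation can separate 2 (continue) from 3 (stop).

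**Working it through.** **1. Classification.** The plan states no figure on this point, so the first check is logical. Apply 4.2 as: both required conditions, and at least one of the three criteria, and not on the exclusion list. Take an event in the first 28 days that is not clearly due to disease.

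| Event | Criterion met | On exclusion list | Counted |
|---|---|---|---|
| Grade 3 lymphopenia, treatment continues | none (hematologic) | no | no |
| Grade 3 lymphopenia, ends treatment | discontinuation | no | **yes** |
| Grade 4 lymphopenia, treatment continues | Grade 4 | yes | no |
| Grade 4 lymphopenia, ends treatment | Grade 4 and discontinuation | yes | **no** |
| Grade 4 neutropenia, not resolved in 14 days | Grade 4 | no (condition fails) | yes |

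Nothing elsewhere in the protocol or the SAP adds a condition to the lymphopenia entry.

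**2. Can the fourth row arise?** Table 3 does not discontinue for a first Grade 4 lymphopenia; it requires a hold and then a reduction of at least 100 mg. Three routes remain.

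- *Long hold (the main route).* No recovery to Grade 1 or baseline within 21 days of the last dose, so 6.6.2 bars restart. The same hold applies to Grade 3, so the same failure to recover would be counted at Grade 3 and not at Grade 4.
- *Expected recurrence.* Restart is barred if recurrence at the same grade is expected. The required dose reduction can itself support the view that it is not, so this route needs recurrence to be expected despite the reduction.
- *Clinical judgment* under 4.7.

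**3. Timing of the long-hold route.** Suppose Grade 4 is found at the Day 15 hematology (window ±2 days, Table 1 notes) and the last dose is that day. Last day on which restart is allowed = day of last dose + 21:

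- Day 13 + 21 = Day 34, which is 34 − 28 = 6 days after the first cycle ends
- Day 15 + 21 = Day 36, 8 days after
- Day 17 + 21 = Day 38, 10 days after

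Section 4.2 requires the event, not the discontinuation, to fall in the first 28 days, so such a case would meet the third criterion. The lead-in review needs only one completed cycle, so for the last subjects enrolled the discontinuation could come after the review.

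**4. When would one uncounted event decide the count?** Given one such event among the 10 subjects, it matters only if exactly 2 of the other 9 are counted. With p the chance that any other subject has a counted toxicity (assumed; the documents give none) and subjects independent:

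P(exactly 2 of 9) = 36 × p² × (1 − p)⁷

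| p (assumed) | 5% | 10% | 15% | 20% | 25% |
|---|---|---|---|---|---|
| P | 0.063 | 0.172 | 0.260 | 0.302 | 0.300 |

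These chances are conditional on the event having occurred. Protocol 1.4 lists lymphopenia among the adverse events seen in Phase 1 but gives no frequency and reports no dose-limiting toxicities, so no unconditional effect on the stopping probability can be derived.

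**The case against.** The strongest reply is that leniency toward lymphopenia is deliberate. Table 3 gives Grade 4 lymphopenia its own row without the 14-day recovery limit set for anemia and neutropenia, and the entry criteria set floors for neutrophils, platelets and hemoglobin but none for lymphocytes. This stands as a reason to exclude Grade 4 lymphopenia that recovers. It does not explain excluding one that ends treatment, which 4.2 otherwise treats as a signal at any grade.

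A second reply is that the harm that matters is caught anyway. A Grade 3 infection following lymphopenia is a Grade 3 non-hematologic event, is not on the exclusion list, and counts. This stands. Only a treatment-ending Grade 4 lymphopenia with no other counted event escapes.

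A third is that the routes are narrow: 6.6.1 says only that a subject held beyond 21 days may be discontinued, and the expected-recurrence route is weakened by the dose reduction. This also stands, although the restart conditions in 6.6.2 are firmer than 6.6.1.

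A fourth is that the SRC can act regardless. It reviews all safety data, its recommendation governs the stop, and 9.3 lets it adjust dose and schedule. This largely stands and is the main reason the effect is small. The discretionary clause in 4.2 is less certain help: it speaks of toxicities not listed above, and Grade 4 lymphopenia is listed. It can also be read as covering anything not listed as unacceptable, which would reach this event.

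A reader might go further and infer that the lead-in stop was unsafe or that a signal was missed. The documents do not support this. They report no such event, and SAP 1.1 records that the SRC reviewed the lead-in and recommended continuing.

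**Conclusion.** The point holds as a drafting defect in a safety-stop definition, and it is minor. On the literal text, a first-28-day Grade 4 lymphopenia that ends treatment is not counted and a Grade 3 one is.

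The effect is at most one subject's difference in the count per event. Given one event, the chance that it is decisive is about 6% to 30%, resting on assumed rates of 5% to 25% for other counted toxicity and on independence between subjects. A reader might take these figures as a change in the probability of stopping. They are not, because the documents give no rate for the event itself.

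A reader might also infer that all four exclusions need overriding. The other three already require resolution or control, so the text does not support extending the criticism to them.

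Nothing in the present trial turns on the point. The lead-in is complete, and SAP 5.7.2 reports that the study was closed for futility after a fourteenth patient was enrolled.

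**What to change.** Change only the lymphopenia entry in 4.2, to read: *Grade 4 lymphopenia, unless it results in permanent discontinuation of SPH4336*. Leave the other three exclusions as written. A Grade 4 lymphopenia that recovers and allows restart stays excluded, so the intended leniency is kept, and the entry then agrees with the third criterion in 4.2.

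The cost is a slightly more sensitive stop and a minor amendment, with the IRB review and regulatory submission described in Protocol 11.2 and 12.2. No new data or procedures are needed. As this study is closed, the practical use is in any later protocol that takes over this definition.
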